# 3.6 Participant Withdrawal

Participants will be allowed to voluntarily withdraw from the study for any reason and at any time. The investigator may withdraw participants from the study in order to protect their safety or if they are unwilling or unable to comply with required study procedures after consultation with the study sponsors and co-sponsors. Participants also may be withdrawn if the study sponsor, government or regulatory authorities, or site IRBs/ECs terminate the study before the planned end date. Reasons for withdrawal from the study will be recorded and a final evaluation will be made if feasible.

Participants who discontinue treatment but remain in the study will continue to be followed-up whenever possible.

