# 4.3 Adherence Assessment

Adherence to the study treatment will be assessed by study coordinator phone call midway through each treatment arm to assess adherence and inventory method to assess remaining medication/placebo at the end of the study. Adherence will be defined as consumption of at least 75% of the prescribed regimen. Up to 36 participants may be recruited to compensate for non-adherence or drop-out with the goal of 10 individuals completing in each treatment arm. Participants will be asked to bring in unused study drugs at each visit to return to IDS.

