## 4.4 Toxicity Management

Currently, the mechanism whereby Coenzyme Q10 and Nicotinamide Riboside may cause harm or toxicity is unknown. There have been studies demonstrating slightly decreasing hemoglobin and potassium in healthy controls treated with NR^13. In the event of moderate or serious adverse effects (as defined in section 6.2) requiring treatment for such conditions as nausea, vomiting, or abdominal pain thought to be related to toxicity from the study drug, the patient will be withdrawn from the study and adverse events reported.

Mild adverse events that do not requiring treatment and are thought to be potentially related to toxicity from the drug will prompt a 50% dose reduction.

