# 4.5 Clinical Management of Pregnancy

All female participants of childbearing age who are sexually active will be asked to use contraception during the duration of the study and for 1 month afterwards as the effects of Coenzyme Q10 and Nicotinamide Riboside on fetal development are not clear.

Any females who become pregnant during the study period will stop taking the study product, but will continue with study procedures with the exception of the MRS procedures.

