### **Procedures/Sample collection:**

An overview of the study visit and procedures schedule is presented in Appendix I. Presented below is additional information on visit-specific study procedures and Table 4.

*Physiologic measurements from cycle ergometry:* The main outcome of this study is aerobic capacity (VO2max) using cycle ergometry. Secondary outcome is muscle performance using measures of total work and work efficiency which will be obtained by cycle ergometry using standard protocol measuring oxygen uptake starting at 0 watts (W) at 60 rotations per minute (rpm) increasing by 30W every 3 minutes until volitional exhaustion adapting a prior protocol used in CKD patients. Approximately 30W of activity is required for grocery shopping and 60W is necessary for household chores. Work efficiency will be calculated as the work performed/energy expended (VO2) above that in cycling 0 watts x 100%. The minimum criteria for a successful efficiency calculation will be a rating of perceived exertion (RPE) of 13 (scale 6-20) or 75% of predicted maximal heartrate. The minimum goal for successfully achieving a VO2max is a RPE of 17 or respiratory exchange ratio≥1. Recovery will consist of pedaling 5 minutes at 10 watts and 60rpm. **Participants should be fasting for at least 6 hrs prior to this test and not exercise for 48hr prior to this test.** 

*PBMC mitochondrial bioenergetic stress test:* Monocytes are specifically selected due the strong correlation of their bioenergetics properties with skeletal muscle and cardiac bioenergetics in the primate model. Blood samples will be process using an established protocol. Sample collection should be coordinated in advance with [name] ([contact]).

*Blood testing for metabolic response profile* (oxidative stress, inflammation, and plasma amino acids, metabolites, and electrolytes). Oxidative Stress and Inflammatory Biomarkers include: C-reactive protein and IL-6 levels will be determined using the automated Abbott FLX C-Reactive Protein Assay and by ELISA, respectively. Plasma

F2-isoprostanes and isofurans will be measured by GC-MS as described by Roberts and Morrow at Vanderbilt University (c/o [name]: [contact]).

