# Week 6, 13, 20 (Visit 2, 3, 4):

The prevention center and [name] lab will be contacted to arrange the primary outcome of resting energy expenditure, aerobic capacity and secondary outcomes of monocyte mitochondrial energetics at the end of each treatment period. Patients will also have fasting blood collection and return a 24hr urine collection. If qualified, they will also receive a repeat MRS at UWMC during the same week. **Patient remain on treatment during these visits to ensure drug effect.** 

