# 6.0 SAFETY MONITORING AND ADVERSE EVENT REPORTING

# 6.1 Safety Monitoring

All adverse events will be followed by the PI and study personnel until the events are resolved, the subject is lost to follow-up, or the adverse event is otherwise explained. At the last scheduled visit, the investigator will instruct each subject to report any subsequent event(s) that the subject, or the subject's personal physician, believes might reasonably be related to participation in this study. The investigator will follow any death or adverse event occurring at any time after a subject has discontinued or terminated study participation that may reasonably be related to this study. An internal audit will take place each month of the trial to insure that everything is well documented.

As each of the first five subjects completes the cross-over, we will submit to the IRB a report on how the drug was tolerated. We will report all side effects, adverse events and subject concerns. In the event that one of the first 5 subjects withdraws from the study for reasons related to the drug, we will report immediately to the IRB via modification.

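### Section 4.4 takes participants out of the study, not only off the drug, after a treated, suspected drug effect: a minor, cheaply avoided loss of later-period VO2max values

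*Combined protocol and SAP*

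**What the plan says.** Section 4.4 (Toxicity Management) sets a graded rule. A mild, untreated effect that may be drug-related halves the dose. For a moderate or serious effect that needs treatment and is suspected to be drug-related, "the patient will be withdrawn from the study and adverse events reported". On the severity scale in 6.2.1, moderate (grade 2) means that the event resolved with treatment, so treated nausea is enough.

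Section 3.6 (Participant Withdrawal) has two relevant sentences. "Participants who discontinue treatment but remain in the study will continue to be followed-up whenever possible" applies to people still in the study. For those withdrawn, "a final evaluation will be made if feasible", with no stated content and no later-period visits.

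Section 4.5 handles pregnancy differently: the participant "will stop taking the study product, but will continue with study procedures", apart from the MRS.

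Section 4.3 allows over-recruitment: "Up to 36 participants may be recruited to compensate for non-adherence or drop-out". Section 7.3, Table 2, plans six sequences of five people, each person to receive NR, CoQ10 and placebo.

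**The concern.** In a parallel-group trial, withdrawal for a drug reaction shortens follow-up in one arm. Here each person is meant to supply all three treatment values. Leaving in one period removes every later period, including values on products that caused no problem. Someone treated for nausea on CoQ10 in period 1 contributes nothing to NR versus placebo.

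The loss is triggered by a judged drug reaction, so it cannot be presumed random. Recruiting up to 36 restores numbers but not the people who reacted. Values that were never collected cannot be recovered by any later analysis. Sections 3.6 and 4.5 already separate stopping the product from leaving the study; 4.4 does not.

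**Working it through.** **The plan's own figures.** Inputs from 7.3: SD of the within-person difference 2.1 ml/kg/min, design effect 2.1 ml/kg/min (1 SD), two-sided 0.05. A paired t-test with noncentral t on n − 1 degrees of freedom gives 34, 16 and 10 for 80% power at 0.5, 0.75 and 1 SD, and 44, 21 and 13 for 90%. All six cells of Table 3 are reproduced.

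**Counts that need no event rate.** Six sequences with two active periods each give 12 placements for a first reaction. The reaction falls in period 1, 2 or 3 in four placements each.

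- Later periods lost: (4 × 2 + 4 × 1 + 4 × 0) / 12 = 1.0 on average.
- The other drug's pair with placebo is complete only when the reaction is in period 3: 4 of 12. In the other 8 it can be kept only if the remaining products are started.
- The reacting drug's own on-drug value is not recovered in any placement.

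**Counts that need a rate.** The documents give none. Assume a probability w per active period, none on placebo, and 30 enrolled. Averaging over the six sequences:

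- Withdrawn: 30 × [1 − (1 − w)²]
- Later-period outcomes lost, of 90: 30 × (2w − w²/3)
- Pairs lost per contrast to that contrast's own drug: 30 × w(2 − w)/2
- Pairs lost per contrast to the other drug: 30 × (4w − w²)/6

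| w | Withdrawn | Later outcomes lost | Own-drug pairs lost | Other-drug pairs lost | Total pairs lost | Pairs left |
|---|---|---|---|---|---|---|
| 2% | 1.19 | 1.20 | 0.59 | 0.40 | 0.99 | 29.01 |
| 5% | 2.93 | 2.98 | 1.46 | 0.99 | 2.45 | 27.55 |
| 10% | 5.70 | 5.90 | 2.85 | 1.95 | 4.80 | 25.20 |

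Only the other-drug losses can be kept as on-drug pairs: 0.40/0.99 = 40% and 1.95/4.80 = 41%. This is an upper bound, because it assumes that every remaining product is started and tolerated. With 10% on each drug and 5% on placebo, each contrast loses 6.06 pairs, of which 1.93 (32%) are recoverable. With 10% on NR only, NR loses 3.0 pairs, none recoverable, and CoQ10 loses 2.0, all recoverable.

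**Power.** At 1 SD it is 98.9% with 20 pairs and 99.8% with 25. At 0.5 SD (1.05 ml/kg/min) it is 75.4% with 30 pairs, 73.9% with 29.0 and 67.3% with 25.2. If every recoverable pair were kept at w = 10% (about 27 pairs), it would be about 71%.

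**Possible bias.** Suppose that a drug's mean effect in the people whose pair is lost but recoverable differs by 1 ml/kg/min from that in the people kept. Losing them shifts the estimate by other-drug losses / (30 − own-drug losses):

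- 2%: 0.398 / 29.41 = 0.014 ml/kg/min
- 10%: 1.95 / 27.15 = 0.072 ml/kg/min

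The standard error is 2.1/√30 = 0.383, so the shift is 0.04 to 0.19 standard errors. To move the estimate by one standard error, the difference would have to be 0.383/0.0718 = 5.3 ml/kg/min at 10%, or about 28 at 2%.

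**The case against.** The case for leaving 4.4 alone has four parts.

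**The effect is small.** A one-standard-error shift at the top rate needs an effect difference of 5.3 ml/kg/min, which is 2.5 times the design effect (5.3/2.1), between people who reacted to the other drug and the rest. This stands, and it is why the point is minor.

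**Numbers are replaced.** If the allowance were spent only on this, 36 × (1 − 4.80/30) = 30.2 pairs per contrast at w = 10%. This stands for numbers. It does not address selection.

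**Recovered values may be weak.** The post-treatment visits are meant to be on drug: "Patient remain on treatment during these visits to ensure drug effect". Section 7.5 unblinds early for an adverse event believed to be treatment-related, which is close to the trigger in 4.4. Once one period is unblinded, only two orders remain possible for the other two. The exercise test is effort-dependent: "increasing by 30W every 3 minutes until volitional exhaustion". All of this lowers the yield below the 40% bound, and such values should not enter the primary estimate unflagged. It does not make collecting them worthless.

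**Withdrawal is a defensible safety choice.** Section 4.4 describes the toxicity mechanism as unknown, and on-drug recovery means starting another product after a suspected reaction. Pregnancy is an imperfect precedent, since it is not a drug reaction. The answer is to leave the next product to clinical judgment; staying in the study for visits does not require taking it.

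A reader might infer that the rule biases the primary result. The documents do not support that: bias needs tolerance to be related to VO2max response, and nothing in them shows or excludes this. Nor do they show that events will be common. Section 8.2 points toward few, although its tolerability statement at higher doses concerns CoQ10 in dialysis patients, in most individuals, and not NR.

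**Conclusion.** The point holds as a minor, cheap improvement. As written, 4.4 removes the person from the study, and 3.6 does not bring that person back into follow-up. The counts of one later outcome lost on average, and 4 of 12 placements with the other pair complete, follow from the design alone. The 1.0 to 4.8 pairs per contrast rest on assumed rates of 2% to 10%, equal for the two drugs and zero on placebo, before replacement; at most about 40% of those pairs could be kept on drug.

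Two further inferences should be resisted. Power at 2.1 ml/kg/min is not at risk, because Table 3 needs only 10 pairs for 80% there; only a smaller target such as 0.5 SD would feel the loss. Nor does the rule discard everything about a withdrawn participant: completed periods have been measured, and the final evaluation may capture the current one. Section 7.6.1 does not say whether incomplete sequences enter the ANOVA, but that is a separate gap and carries no weight here.

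Loose wording in 4.4 is possible. If only stopping the drug was meant, the same edit makes that clear.

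**What to change.** - **Section 4.4:** replace withdrawal from the study with stopping the current study drug. The participant stays in the study under 3.6 and attends the remaining scheduled outcome visits if willing and fit for exercise testing. Starting the next period's product is a clinical decision. Leaving the study is reserved for safety or withdrawn consent.
- **Section 6.1:** the immediate IRB report is tied to the event that "one of the first 5 subjects withdraws from the study for reasons related to the drug". Extend it to drug-related stopping of study drug, so that the change in 4.4 does not weaken the safety trigger.
- **Analysis:** flag values measured off drug or after unblinding, and use them only in a sensitivity analysis. Section 7.5 can stay as it is.

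The cost is wording in two sections plus a short analysis rule, with no visits beyond those already scheduled. The downside is that some added values will be off drug or unblinded and so will not help the primary estimate.

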### 3.5 Participant Retention

Every effort to retain enrolled participants will be made throughout the duration of the study in order to reduce bias related to loss to follow-up. Strategies for participant retention include:

- Thorough explanation of the importance of all 3 study treatment groups to the overall success of the study
- Detailed explanation of the study visit schedule and procedural requirements during the informed consent process, with re-emphasis at the end of each study visit
- Use of appropriate and timely visit reminder mechanisms. This includes midtreatment phone call to assess participant adherence to regimen and remind participants of subsequent follow up visits
- Compensating participants for their time and effort in the study
- Immediate and multifaceted follow-up on missed visits

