# Baseline visit and Post-treatment visits (2, 3, 4)

The participant will have been required to fast for at least 6 hrs prior to each visit and abstain from caffeine or smoking before bicycle ergometry testing. Patient should avoid exercise 48hours prior to cycle ergometry. Treatment will be dispensed after cycle

ergometry at baseline and post-treatment visits 2,3 and 4. The following data will be obtained:

- Vital signs.
- Fasting blood collection for banked plasma and peripheral blood mitochondrial energetics.
- Anthropometrics (height and weight and waist to hip ratio)
- Urine pregnancy test will be given to women of child-bearing potential
- Resting energy expenditure (REE) and cycle ergometry will be performed at the Prevention center.
- The optional MRS and Muscle Fatigue tests will occur at the diagnostic imaging center at UWMC at baseline and in the same week of visits 2, 3 and 4 while patient remains on study drug. Patient should wait avoid heavy exercise for 48hrs before MRS.
- Questionnaires will be administered (PROMIS fatigue short form 17, PROMIS physical function short form 20a, and Kansas city heart failure questionnaire)

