# Mid-intervention visits/phone calls:

All subjects will receive a phone call by study coordinators 4 weeks (mid-way) into each intervention arm to confirm patients are taking their treatment/placebo medication in order to ensure adherence. They will also receive a reminder of their subsequent visits.

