# Washout (week 7 and 14):

After the second visit, the participant will undergo a 1 week washout period prior to initiating the subsequent treatment arm for another 6 week period.

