# **Optional Procedures:**

A subset of participants (N=20) may choose to undergo the following muscle imaging procedures. Subjects will go to the UW DISC lab for testing +/-3 days from each scheduled visit (Baseline – visit 4).

*Magnetic Resonance Spectroscopy:* Leg MRS will serve as a secondary outcome and optional. All participants will be offered the option to receiving leg MRS. As mentioned above, only 4 MRS will be obtained as part of this study (at Baseline, visit 2, 4 and 6). MRS will be used to measure phosphorylation capacity (ATPmax) tibialis anterior leg skeletal muscle. These functional tests assist to perturb the cell physiological state in order to measure the contents and dynamics of key metabolic compounds important in mitochondrial energy flux. P MRS is reliable with a documented coefficient of variation for oxidative phosphorylation of 5.1% and has a strong correlation with V02max. Scheduling of this test should be coordinated with [name] ([contact]).

*Muscle Fatigue:* We will test muscle fatigability at each follow-up visit. We will test the TA (tibialis anterior) leg muscle and determine the isometric force generated at 70% of maximal voluntary contraction (MVC) against a force transducer. Using labview software to measure and record the force-time waveform of each contraction we will initiate the protocol at 50 contractions per minute at 70% MVC for one minute. At each 1 minute increment will increase the contraction rate by 10 contractions per minute and reassess the subjects relative perceived exertion on a scale of 1-10 until the patient can no longer maintain the contraction waveform.

				Treatment arm 1 (6wk +/-7d)	Treatment arm 2 (6wk +/-7d)	Treatment arm 3 (6wk +/-7d)
	Screen Day -28	Baseline	Optional MRS visit	Day 1 Visit 2 Week 6 (+/-7d)	Wk 8 Visit 3 Week 13 (+/-7d)	Wk 15 Visit 4 Week 20 (+/-7d)
Time	1-1.5hr	3hr	1-2hr	3hr	3hr	3hr
Location	PC	PC	UWMC	PC	PC	PC
Compensation	\$10	\$50	\$50	\$100	\$100	\$100
Consent	Х					
Practice bicycle	Х					
Screeninglabs	Х					
Medical history		Х				
Medicine inventory		Х				
Vital signs/Anthro	Х	Х		Х	Х	Х
Product dispensed		Х		Х	Х	
Assess AEs				Х	Х	Х
Bicycle Vo2max/work		Х		Х	Х	X
REE		Х		Х	Х	Х
PBMC bioenergetics**		Х		Х	Х	Х
31P MRS (subgroup)*			Х	X (UWMC)	X (UWMC)	X (UWMC
mRNA (paxgene)		Х		Х	Х	X
Blood		Х		Х	Х	X
Urine		Х		Х	Х	X
Drug level/NAD		Х		Х	Х	X
PROMIS Fatigue/PF PRO	landout	Х		Х	Х	Х

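### Adverse events are asked about on schedule only at the end of each treatment period, so within a period the dose-reduction rule for mild events depends on what the participant reports

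*Combined protocol and SAP*

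**What the plan says.** **The rule.** Section 4.4 (Toxicity Management) separates two cases. Moderate or serious events that need treatment and are attributed to the drug lead to withdrawal. Mild events that need no treatment and are "thought to be potentially related to toxicity from the drug will prompt a 50% dose reduction". Section 6.2.1 grades as mild an event that needed no treatment.

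**Scheduled AE assessment.** Table 1 marks it at visits 2, 3 and 4 only (weeks 6, 13 and 20). Section 5.0 places these visits at the end of each period and adds "Patient remain on treatment during these visits to ensure drug effect". Afterwards "the participant will undergo a 1 week washout period prior to initiating the subsequent treatment arm". Optional spectroscopy is done "for testing +/-3 days from each scheduled visit", and "while patient remains on study drug".

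**The contact inside a period.** Coordinators phone each participant 4 weeks into each period. Three sections describe the call:
- Section 5.0, Mid-intervention visits/phone calls: "to confirm patients are taking their treatment/placebo medication in order to ensure adherence", plus a reminder of later visits.
- Section 4.3: "Adherence to the study treatment will be assessed by study coordinator phone call midway through each treatment arm to assess adherence".
- Section 3.5: "midtreatment phone call to assess participant adherence to regimen and remind participants of subsequent follow up visits".

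**The other route.** Section 6.2.1 gives participants a telephone number and instructs them to report any AE. It also says that safety information is first gathered by interview, without saying when, and makes the research coordinator responsible for collecting clinical data.

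**The concern.** A dose reduction is useful only while the product under suspicion is still being taken. In this crossover each participant receives each product once (Table 2), so a reduction decided after a period has closed cannot reach the product that prompted it. The only scheduled AE inquiries come at that closing point.

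The events covered by the rule need no treatment by definition, so they are unlikely to come to staff attention unless the participant raises them. A mild event that goes unreported continues at full dose to the end of the period. It is then recorded from memory over a whole period, plus the preceding washout in periods 2 and 3. The tolerability reports that section 6.1 promises the IRB for the first five completers would rest on the same recall. Section 4.4 itself says that the mechanism of any harm from these agents is unknown, which is a reason to ask earlier.

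**Working it through.** The plan gives no figure to reproduce. The check places every planned contact on the timeline.

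**Inputs**
- Period length: 6 weeks ± 7 days (section 4.1, Table 1). Section 2.3 gives 56 days instead, so both are carried through.
- Washout: 1 week (section 5.0).
- AE inquiries: weeks 6, 13 and 20 (Table 1).
- Call: 4 weeks into each period (section 5.0), or midway (section 4.3), which is week 3 of a 6-week period.
- Daily tablets: 4 of NR type, 2 of CoQ10 type (section 4.1).
- Adherence threshold: 75% (section 4.3).

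**1. Scheduled AE inquiries before the end of a period.** 0 in each of 3 periods.

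**2. Suspected product left at the first scheduled inquiry.** About 0 days, or up to about 3 days where spectroscopy follows the visit.

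**3. Time left if AEs are asked about on the call** (period length minus call time)

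| Period | Call | Time left | Share |
|---|---|---|---|
| 6 weeks | week 4 | 6 − 4 = 2 weeks (5 − 4 = 1 to 7 − 4 = 3) | 2/6 = 33% |
| 6 weeks | week 3 | 6 − 3 = 3 weeks (5 − 3 = 2 to 7 − 3 = 4) | 3/6 = 50% |
| 8 weeks | week 4 | 8 − 4 = 4 weeks | 4/8 = 50% |

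**4. Longest look-back between AE inquiries.** The washout counts from period 2 on, because visits 3 and 4 look back to the previous visit.

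| | Now | With a week-4 question |
|---|---|---|
| Period 1, 6 weeks | 6 | max(4, 2) = 4 |
| Periods 2 and 3, 6 weeks | 1 + 6 = 7 | max(1 + 4, 2) = 5 |
| Period 1, 8 weeks | 8 | max(4, 4) = 4 |
| Periods 2 and 3, 8 weeks | 1 + 8 = 9 | max(1 + 4, 4) = 5 |

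**5. Share of the full-dose amount taken by a participant halved at week 4**
- 6 weeks: (4 + 0.5 × 2)/6 = 83%
- 5 weeks: (4 + 0.5 × 1)/5 = 90%
- 7 weeks: (4 + 0.5 × 3)/7 = 79%
- 8 weeks: (4 + 0.5 × 4)/8 = 75%

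For comparison, section 4.4 already accepts a reduction after an early phone report. At the end of week 1 that gives (1 + 0.5 × 5)/6 = 58%, or (1 + 0.5 × 7)/8 = 56%.

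**6. Halving with whole tablets.** NR goes from 4 × 250 mg to 2 × 250 mg = 500 mg daily, still twice a day. CoQ10 goes from 2 × 600 mg to 1 × 600 mg, which is once a day.

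**The case against.** **Reporting within a period is already planned.** Participants are instructed to phone in any AE, and all severities are documented. This stands: the route exists, and relying on it for grade 1 events is defensible. But it starts with the participant, and nothing scheduled backs it up.

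**The evidence is silence.** A reader might infer that coordinators will not ask about AEs on the call. The documents do not support that. Sections 3.5 and 4.3 mention the call only for their own topics, Table 1 has no column for it, and the interview in section 6.2.1 has no stated timing and could take place there. What can be said is that AE questions on the call are not required. Whether they are asked would then depend on the individual coordinator.

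**Section 4.4 does not limit the reduction to the current product.** True, but a reduction carried into the next period would act on a different treatment.

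**More half-dose participants at the VO2max visit could weaken the drug effect that the plan wants present there.** This is a real cost, and it may fall unequally across treatments. Section 4.4 already accepts it for reported events, and a week-4 reduction removes less exposure than an early one.

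**The gain is limited.** Also true. The call leaves 1 to 3 weeks of a 6-week period, and questions cannot detect the falls in hemoglobin and potassium that section 4.4 mentions for NR. The first-five reports are made after the crossover is complete, so they receive all scheduled assessments either way; only the recall improves.

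**Conclusion.** The point holds as a minor safety improvement. As written, the schedule has no AE inquiry at a time when the reduction can still act to any useful extent on the suspected product. Within a period the rule works only through participant reports, by phone as instructed or by mention on the call. A question on the call would give the rule about 2 of 6 weeks (1 to 3 with the window), or 4 of 8, and would shorten the longest look-back by 2 weeks (by 4 with 56-day periods).

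The conclusion is the same for 6-week and 56-day periods. It assumes that the plan is followed as written and that a reduction is meant for the product suspected.

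A reader might go further and infer that participants will be lost or the primary result distorted. The documents support neither. No rule withdraws a participant for a mild event, section 3.6 keeps following those who stop treatment, and the frequency of mild related events is not given. The number of participants affected is therefore unknown.

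**What to change.** Add a short standard AE question set to the existing mid-period call in section 5.0, and add that contact to Table 1 with AE assessment marked in all three periods. A reduction can then be given as a telephone instruction in whole tablets, for placebo too, without an extra visit.

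Two wording points belong with it:
- Count adherence against the reduced dose. Counted against the full dose, a week-4 reduction leaves 83% over 6 weeks but exactly the 75% threshold over 56 days, and an end-of-week-1 reduction (58% or 56%) would fail it.
- State that halved CoQ10 is 600 mg once daily.

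Optionally, section 4.4 could say that a reduction applies to the product in use when the event began. The next product would start at full dose unless the event is unresolved after washout or began during it, when the investigator decides.

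**Cost.** The calls already take place: 30 × 3 = 90, or 36 × 3 = 108 if 36 are recruited. At an assumed 3 to 5 minutes each, this adds 4.5 to 7.5 hours (5.4 to 9.0 hours) of coordinator time over the trial, plus one form page and one table column. More mild events will be recorded in all three treatments, and some more participants will be tested on half dose.
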